9.3.5 Subject numbering

An Identification (ID) number will identify subjects, which is a combination of the specified site number and a sequential number assigned by the sponsor. Subject initials will not be used on case report forms.

9.4 Procedures

This section provides a description of all the clinical-study-related procedures that subjects undergo during the clinical study. Table 1 lists a summary of scheduled assessments. The clinical-study-related procedures do not require additional radiation compared to a traditional VVIR lead implant and conform to standard of care for pacemaker subject management with the exception of femoral vein access instead of cephalic, axillary, or subclavian vein access.

Sponsor representatives may assist the Investigator in assessing pacemaker performance (for example pacing and sensing performance), downloading diagnostic information, and programming pacemaker parameters. Sponsor representatives may also assist the team in equipment setup prior to and during a procedure.

9.4.1 Enrollment assessment

The Investigator will not start any study-specific procedures or alterations of subject care until the informed consent process has been completed and Investigator obtains a signed Informed Consent Form. To determine eligibility, some screening procedures may be necessary. If any of these tests do not fall within the Investigator's standard clinical practice, they will be required for subjects to be enrolled in the clinical study.

During this visit, investigation team will collect medical history data.

In addition:

- For subjects who were previously implanted with a Nanostim LCP at one of the selected sites involving physician trainers and study leaders, investigation team will collect implant procedure data, pre-discharge data and any study related events (Adverse Event, Device Deficiency, additional visit, etc.).
- For pre-CE mark LEADLESS study subjects, investigation team will collect any study related adverse events.

9.4.2 Implant procedure

[figure not shown]
Medications

Investigator will administer all medications per hospital standard of care for pacemaker implant and femoral venous catheterization procedures. Anticoagulation medications may be used with the implantation of the LCP per physician's discretion. Investigator will record all medications given during procedure on subject's medical record.

The LEADLESS Observational Study

The LEADLESS Observational Study

9.4.3 Post-procedure assessments

This section does not apply to subjects who were previously implanted with a Nanostim LCP.

The follow-up period is sufficient to demonstrate performance. Additionally, during this follow-up period, Sponsor will identify and assess any risks associated with adverse device effects (ADEs). Subjects will continue with follow-up visits consistent with the institution's standard of care for pacemakers. Table 1 lists the schedule of assessments.

Investigator will assess enrolled subjects, who have an LCP implant attempted but whose implant procedure cannot be completed, for AEs occurring up to 30 days post implant attempt.

Investigator will report any subjects who require LCP revision after implantation.

- If the subject has the Nanostim™ LCP removed at any time during the study, and the subject will receive another Nanostim LCP, the investigator will continue following the patient in the study.
- If the subject has the Nanostim™ LCP removed or deactivated at any time during the study, and the subject will not receive a replacement Nanostim™ LCP, the investigator will assess the subject for AEs occurring up to 30 days post revision.

Access-site management during hospital stay

Investigator will manage access sites per standard of care. Investigator will assess and document any post-procedural access-site bleeding event based on the following grading system.

ACCESS-SITE OOZING: Superficial bleeding of a cutaneous or subcutaneous origin characterized by diffuse localized bleeding and controlled with minimal care (e.g., application of manual pressure, application of sandbag).

ACCESS-SITE HEMATOMA: A localized collection of extravasated blood in subcutaneous tissue at the access site that does not require intervention. A metric ruler should be used to measure the widest portion of the hematoma.

ACCESS-SITE HEMATOMA REQUIRING INTERVENTION: A localized collection of extravasated blood in subcutaneous tissue at the access site that is considered life threatening and requires emergency wound exploration (e.g., acutely expanding hematoma, acute leg pain/numbness/swelling) and/or prolongation of hospital stay.

ACCESS-SITE RE-BLEEDING: Localized bleeding at the access site that occurs after hospital discharge. These bleeds are typically associated with an event (e.g., fall, attempted suture removal, physical activity).

Pre-Discharge Visit

Investigator will use medical judgment and provide institutional standard of care for post-pacemaker-implant monitoring.

During this visit, investigation team will:

- Assess for adverse events, device deficiencies and deviations to this observational study plan,
- Check pacing capture threshold, R-wave amplitude, pacing impedance, and battery voltage,
- Adjust programmable parameters of LCP, as needed

9.4.4 90-day follow-up visit (within 60-120 days post-implant)

This section may apply to subjects who were previously implanted with a Nanostim LCP if the visit is within the 90-day visit window (within 60-120 days post implant).

All subjects will return to the implant center at the investigation site for a 90-day follow-up visit. During this visit, investigation team will:

- Assess for adverse events, device deficiencies and deviations to this observational study plan,
- Check pacing capture threshold, R-wave amplitude, pacing impedance, and battery voltage, and
- Adjust programmable parameters of LCP, as needed, and

9.4.5 6-month follow-up visit (within 5-7 months post-implant)

This section may apply to subjects who were previously implanted with a Nanostim LCP if the visit occurred within the 6-month visit window (within 5-7 months post implant).

All subjects will return to the implant center at the investigation site for a 6-month follow-up visit. During this visit, investigation team will:

- Assess for adverse events, device deficiencies and deviations to this observational study plan,
- Check pacing capture threshold, R-wave amplitude, pacing impedance, and battery voltage, and
- Adjust programmable parameters of LCP, as needed.

9.4.6 Every 6-month follow-up visits thereafter (until the last enrolled subject has completed a 5 year visit)

All subjects will return to the implant center at the investigation site every 6 months for a follow-up visit after the 6-month follow-up visit until the last enrolled subject has completed a 5 year visit. During this visit, investigation team will:

- Assess for adverse events, device deficiencies and deviations to this observational study plan,
- Check pacing capture threshold, R-wave amplitude, pacing impedance, and battery voltage, and
- Adjust programmable parameters of LCP, as needed.

9.4.7 Holter data collection visit

This section does not apply to subjects who were already implanted with a Nanostim LCP.

24-hour Holter data will be collected in approximately 25 subjects, any time after the first 30 days of follow-up.

9.4.8 Additional visit(s)

If a subject returns to the implant center at the investigation site for a clinically-warranted unscheduled visit, investigation team will:

- Assess for adverse events, device deficiencies and deviations to this observational study plan,
- Check pacing capture threshold, R-wave amplitude, pacing impedance, and battery voltage, and
- Adjust programmable parameters of LCP, as needed.

9.5 Monitoring plan

On site-monitoring shall be performed during the clinical investigation in order to guarantee adherence to all applicable regulations, the clinical investigation plan and the signed Clinical Study Agreement. By monitoring, the Sponsor can also verify the accuracy of data collected on the accompanying Case Report Forms (CRFs: electronic or paper) throughout the duration of the study.

Monitoring is necessary to ensure adequate protection of the rights and safety of human subjects involved in the clinical investigation and the quality and integrity of the data obtained during the investigation. The sponsor will at the same time assess the investigational site and study team on staffing and facilities to ensure the investigation can continue in a safe and effective fashion.

During the monitoring visits, data reported on the CRF shall be reviewed as specified in the monitoring plan. (Refer to section [9.5.2](#)).

9.5.1 Designated Monitors

Only monitors qualified by education, training and experience, which have been trained on the Clinical Investigation Plan, CRF content, Monitoring Plan, relevant requirements and informed consent process will be allowed to perform monitoring activities during this clinical investigation. The monitor's qualifications and training will be documented by the sponsor. A list of monitors is available upon request.

9.5.2 Monitoring Plan

Prior to the start of the site monitoring activities for this clinical investigation, a project specific Monitoring Plan (MP) will be created and will be available upon request.

At a minimum, the Monitoring Plan will include the following:

- Required activities
- Frequency of monitoring visits
- Visit Requirements
- Procedures for securing site compliance
- Monitoring report content and timelines
- Close-out procedures

The Monitoring Plan may be updated as appropriate. All revisions will be tracked.

9.5.3 Competent Authority (CA) Inspections

The investigator and/or delegate should contact the sponsor immediately upon notification of a CA inspection at the site. A clinical monitor will assist the investigator and/or delegate in preparing for the audit.

An investigator who has authority to grant access shall permit authorized CA employees, at reasonable times and in reasonable manner, to enter and inspect any establishment where devices are held (including any establishment where devices are used or where records or results are kept).

An investigator, or any person acting on behalf of such a person with respect to the investigation, shall permit authorized CA employees, at reasonable times and in reasonable manner, to inspect and copy all records relating to the investigation.

An investigator shall permit authorized CA employees to inspect and copy records that identify subjects, upon notice that CA has reason to suspect that adequate informed consent was not obtained, or that reports required to be submitted by the investigator, to the Sponsor or EC/IRB have not been submitted or are incomplete, inaccurate, false or misleading.

10 STATISTICAL CONSIDERATIONS

10.1 Statistical design, method and analytical procedures, sample size, level of significance and power

Refer to § 6.1 for a discussion of statistical design for the primary objective.

The sample size also permits application of the normal approximation to distributions of means. This enables the clinical study to provide confidence intervals derived from sample means and standard deviations of performance parameters (§9.1.2).

Table 2: Summary of the objectives and the analytical procedures of the clinical investigation

Objective	Type of objective	Clinical testing
180-day Complication-free rate (CFR)	Primary safety	Confidence Interval
5-year CFR	Supplementary	Confidence Interval
Implant-success rate (ISR)	Additional data	Descriptive statistics
LCP Performance ¹	Additional data	Descriptive statistics at all visits

Descriptive statistics will provide mean, standard deviation, and a two-sided 90 % confidence interval.

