3 STUDY SYNOPSIS

Title	Nanostim study for a leadless cardiac pacemaker system – the LEADLESS observational study
Study Device	Leadless cardiac pacemaker (LCP) system
Regulatory Classification of the Study Device	Active Implantable Medical Device (AIMD) 90/385/EEC.
Study Objective	
To confirm clinical performance and safety of the Nanostim leadless cardiac pacemaker system, within its intended use and according to its instructions for use, by confirming the acceptability of identified risks and detecting emerging risks on the basis of factual evidence.
 
A sub-set of patients enrolled in this study will be used to meet the Post Market Clinical Follow-Up (PMCF) requirement for CE mark. Once this sub-set of patients is enrolled and followed for 6 months, a report will be submitted indicating completion of this requirement.

Number of Institutions	Up to 100 study sites. 
Number of Subjects	A total of 1000 patients will be enrolled. The PMCF will be complete when data from 300 patients followed for 6 months are obtained.
Study Population	Subjects who are at least 18 years old, and who are indicated for a VVI(R) pacemaker Subjects who participated in the pre-CE mark LEADLESS study, in the Nanostim Delivery Catheter pre-CE mark study or were implanted with a Nanostim Leadless Cardiac Pacemaker within 3 months of the study start at one of the selected sites involving physician trainers and study leaders can be enrolled in this study. 

The LEADLESS Observational Study

Schedule of Assessments	
Enrollment, Implant, Pre-discharge, 90-day, 6-month and every 6-month follow-ups thereafter (until the last enrolled subject has completed a 5-year follow-up visit).
 
The PMCF requirement will be met when the 300th patient has completed the 6 month follow-up visit.

Study Design	Prospective, non-randomized, single-arm, multicenter, post-market study
Primary Endpoint	The primary safety endpoint is to evaluate a 180-day complication-free rate, where a complication is defined as a serious adverse device effect (SADE).
Additional Data	
- Pacing and sensing performance- All adverse events- Implant success rate- Procedure time- Time to discharge

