6 JUSTIFICATION FOR THE STUDY DESIGN

This is a study of a CE-marked product within its approved indications, in accordance with its instructions for use. Before this study begins, the manufacturer will have demonstrated conformance of the device with essential requirements, and a positive benefit/risk balance, through pre-clinical testing and clinical evaluation, including a proper pre-market clinical investigation. However, [REDACTED]

[REDACTED] important information about potential residual risks can be gathered in this post-market observational study:

[figure not shown]
- This study may detect rare complications that only become apparent after wider-spread use of the device, again because of the increased sample size and number of physicians implanting the system in this post-market study.
- This study may provide stability data on long-term performance of the study device, through 5 years follow-up.

Consequently, the Sponsor has designed a prospective, non-randomized, single-arm, multicenter, post-market, observational study. This study will follow 1000 patients and will be completed when the last patient reaches the 5 year follow-up visit. The design will include a study population who are at least 18 years of age and who are indicated for a VVIR pacemaker.

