6.2 Long-term performance data

The study will observe and report the following performance data at 5 years after implant: pacing threshold, pacing impedance, R-wave amplitude and battery voltage.

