9.1.2 Primary, secondary, supplementary endpoints and additional data

- Primary Safety Endpoint: Freedom from complications (serious adverse device effect) at 180 days. Safety will be measured by reporting the complication rate, defined as SADE (§16.4).
- Supplementary Endpoints: Freedom from complications (serious adverse device effect) at 90 days and 5 years.
- Additional Data:
 - Right ventricular pacing and sensing functions (pacing threshold, R-wave amplitude, battery voltage and pacing impedance performance) at each of the study visits
 - All adverse events
 - Implant success rate,
 - Defined as the number of subjects leaving the implant procedure with an implanted and functioning LCP device, divided by the number of subjects in whom implantation is attempted.
 - Procedure time,
 - Defined as the time from delivery catheter and LCP insertion to removal of the delivery system.
 - Time to discharge,
 - Defined as the time from introducer sheath removal to discharge.

9.1.3 Equipment to be used for assessing the clinical study variables and arrangements for monitoring maintenance and calibration

Device performance is primarily measured with a Nanostim programmer and the implanted Nanostim LCP. The Nanostim programmer does not require scheduled maintenance or calibration.

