9.3.4 Recruitment and enrollment

Candidates for this clinical study include subjects indicated for a VVI(R) pacemaker. Pre-enrollment records will include evidence of diagnosis indicating need for VVI(R) pacemaker. Preoperative screening to confirm the diagnosis is not considered part of the clinical study; however, the informed consent form will inform the subject that their medical history records used to confirm diagnosis will be incorporated into the study record.

Enrollment begins when the subject provides written informed consent and agrees to participate in the clinical study. A total of 300 subjects are needed to meet the 6-month follow-up sample size. Additional subjects will be enrolled until approximately total 1000 subjects are enrolled and everyone will be followed for at least up to 5 years post implant to document the long term performance of the system.

Patients who participated in the pre-CE mark LEADLESS study, the Nanostim Delivery Catheter pre-CE mark study or were implanted with a Nanostim Leadless Cardiac Pacemaker within 3 months of the study start at one of the selected sites involving physician trainers and study leaders can be enrolled.

For the pre-CE mark LEADLESS study subjects, the data collection will start after consent is obtained and will include any study related adverse event documentation after the subject exited the pre-CE mark LEADLESS study.

For the Nanostim Delivery Catheter pre-CE mark subjects, the data collection will start after consent is obtained.

For subjects who were implanted with a Nanostim Leadless Cardiac Pacemaker within 3 months of the study start at one of the selected sites involving physician trainers and study leaders, the data collection will start after consent is obtained and will include implantation procedure, pre-discharge visit and any study related events (Adverse Event, Device Deficiency, additional visit, etc.).

Additionally, 24-hour Holter data will be collected in approximately 25 subjects any time after the first 30 days of follow-up.

Sponsor anticipates that the clinical study will be completed within 6 years.

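### Device stability is to be read from separate visit means, which give no interval for within-device change and, after year 5, describe only earlier enrollees

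*Combined protocol and SAP*

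**What the plan says.** Section 9.1.2 lists the performance data as "Right ventricular pacing and sensing functions (pacing threshold, R-wave amplitude, battery voltage and pacing impedance performance) at each of the study visits". They are classed as additional data, without a hypothesis. Section 6 gives a longitudinal purpose: "This study may provide stability data on long-term performance of the study device, through 5 years follow-up". Section 6.2 names one long-term reporting point: "The study will observe and report the following performance data at 5 years after implant".

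The summary table in section 10.1 assigns LCP performance "Descriptive statistics at all visits", and the line below it defines the content: "Descriptive statistics will provide mean, standard deviation, and a two-sided 90 % confidence interval". The visible text names no within-subject change, repeated-measures model or breakdown by cohort. Section 10.2 has subgroup analysis in its title but specifies none.

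Four groups can enter:

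- **De novo implants.** They have the full visit schedule.
- **Subjects implanted within 3 months of study start at selected sites.** Their implant and pre-discharge data are collected at enrolment (sections 9.3.4 and 9.4.1).
- **Pre-CE LEADLESS subjects.** Their schedule in the synopsis has no implant or pre-discharge visit, and has 90-day and 6-month visits only if these fall in the window.
- **Delivery Catheter pre-CE subjects.** "For the Nanostim Delivery Catheter pre-CE mark subjects, the data collection will start after consent is obtained".

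Section 9.4.6 has subjects return "every 6 months for a follow-up visit after the 6-month follow-up visit until the last enrolled subject has completed a 5 year visit". Section 9.3.3 sets a minimum of 5 years for each subject.

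**The concern.** Whether a pacing threshold or battery voltage is stable is a question about the same device at two times. A row of visit means answers a different question: what the average was among those measured at each visit. Two such means with their own intervals do not give an interval for the change, because the correlation between a subject's readings is not used.

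The set of subjects behind each mean also shifts by design, even if no device fails and nobody drops out. Pre-CE subjects are absent from the first readings and present later. After year 5, follow-up continues only for those enrolled early enough. If these groups differ in their usual readings, a reader comparing visit means could see a drift that no device has undergone, or miss one that has occurred. The visit-wise intervals would not reveal this.

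**Working it through.** **Inputs from the documents.** "A total of 1000 patients will be enrolled" (synopsis). First enrolment is December 2013 (month 0), last enrolment November 2018 (month 59) and last visit November 2023 (month 119), all from the synopsis. The interval is two-sided 90% (section 10.1), so z = 1.645.

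**The plan's own figure.** Last enrolment plus 5 years is 59 + 60 = 119 months, which is November 2023. The synopsis dates agree with the 5-year rule.

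**Assumptions.** Accrual is linear over 59 months. The first third enrolled differ from the rest by d SD, and no device changes. Half-widths are shown with 60% of those due still measured, and with all of them measured.

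**Formulas, for year y after implant.**

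- Share due: c = min(59, 119 − 12y)/59.
- Share of the first third among those due: f = min(1, (1/3)/c).
- Shift of the visit mean: (f − 1/3) × d.
- Half-width: 1.645/√(1000 × c × r), with r = 0.6 or 1.

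| Year | c | f | Shift, d = 0.3 | Shift, d = 0.2 | Half-width, r = 0.6 | Half-width, r = 1 |
|---|---|---|---|---|---|---|
| 5 | 59/59 = 100% | 33.3% | 0 | 0 | 0.067 | 0.052 |
| 6 | 47/59 = 80% | 41.8% | 0.026 | 0.017 | 0.075 | 0.058 |
| 7 | 35/59 = 59% | 56.2% | 0.069 | 0.046 | 0.087 | 0.068 |
| 8 | 23/59 = 39% | 85.5% | 0.157 | 0.104 | 0.108 | 0.083 |
| 9 | 11/59 = 19% | 100% | 0.200 | 0.133 | 0.156 | 0.120 |

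Shifts and half-widths are in SD units. At r = 0.6 the 0.3 SD shift exceeds the half-width at years 8 and 9, and the 0.2 SD shift never does, though only just at year 8. That second result depends on r: with everyone measured, 0.2 SD also exceeds the half-width at years 8 and 9, and 0.3 SD about equals it at year 7.

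**Follow-up beyond year 5.** The mean excess is 59/2 = 29.5 months = 2.46 years, out of a mean of 5 + 2.46 = 7.46 years. That is 2.46/7.46 = 33% of scheduled follow-up.

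**Up to year 5.** All de novo subjects are due at every visit, so enrolment era contributes nothing. Only pre-CE subjects change the mix, and their number is not given. If they are 3% to 10% of the total and differ by 0.2 to 0.3 SD, the contrast between pre-discharge and 5 years moves by 0.03 × 0.2 = 0.006 SD to 0.10 × 0.3 = 0.03 SD. Both are below the 0.052 SD half-width at n = 1000. A more extreme assumption, 200 of 1000 and 0.5 SD, gives 0.2 × 0.5 = 0.10 SD.

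**Check by simulation.** There was no true change, a linear 0.5 SD difference from first to last enrolment, 50 late-entry subjects among 1000, and 4,000 repetitions. The difference of separate visit means from pre-discharge averaged 0.012 SD at 60 months, 0.113 SD at 84 and 0.212 SD at 108. The paired within-subject change averaged 0.001 SD or less at all three.

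**Precision.** The standard error of a paired change, relative to that from two independent means, is √(1 − ρ). For an assumed ρ of 0.5 to 0.7 this is 0.71 to 0.55.

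**The case against.** Performance is additional data. No trend test or comparison between visits is planned, and each visit mean validly describes the subjects seen at that visit; a misleading contrast is one that the reader would have to draw. Nothing prevents the sponsor from producing change tables, since readings are taken at every visit. The stated stability aim ends at 5 years, and every shift that exceeds the interval at 60% measured lies at year 8 or later. Section 5.1.3 limits the study to one variant each of pacemaker and delivery catheter, and eligibility is common to all, so a difference between eras is not obvious.

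Most of this stands, and it limits the point to a low-priority improvement. It does not supply an interval for change within the 5-year horizon, and that gap depends on no era difference at all.

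A reader might go further and infer that different cohorts supply the early, middle and late visits, so that era differences will show up as drift. The documents do not support that. Sections 9.3.3 and 9.3.4 have every subject followed for at least 5 years, so de novo subjects from all eras are due at every visit to year 5. The drift also needs a real difference between eras, which the documents neither show nor exclude.

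The calendar is itself uncertain. Section 9.3.4 expects completion within 6 years, whereas the synopsis dates span 119/12 = 9.9 years. With 6 years in total and a 5-year minimum, enrolment would last about one year and the post-year-5 question would nearly disappear.

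**Conclusion.** The point holds as a modest one. For a stated stability aim, the visible plan gives no estimate or interval for within-device change, and this applies at year 5 as much as later. The change in mix is a secondary matter. It is probably small up to year 5, at 0.006 to 0.03 SD under the assumed cohort share and difference. It is potentially misleading after year 5, where a 0.3 SD difference for the first third enrolled would exceed the 90% half-width from about year 8, while 0.2 SD would stay inside it, if 60% of those due are still measured.

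The late-visit figures rest on linear accrual, on the synopsis dates and on an era difference that is supposed rather than observed. The half-width of one visit mean is a yardstick here, not a test of the difference between two visits. Parts of section 6 are blacked out, so the statement is about the visible text. Loss of subjects through death, dropout or device removal is a separate matter, and paired change does not cure it.

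**What to change.** In section 10.1:

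1. Add mean within-subject change with a two-sided 90% CI for threshold, R-wave amplitude, impedance and battery voltage, from the pre-discharge reading to each later visit, in subjects with both readings.
2. Include subjects implanted within 3 months of study start in that analysis, since their pre-discharge data are collected. Show pre-CE LEADLESS and Delivery Catheter subjects separately, from their first in-study reading.
3. Keep the visit-wise means, with n by cohort at each visit.
4. For visits after year 5, show the same subjects' earlier readings beside the later mean, and draw no trend from unmatched means.

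Reconcile the 6-year completion statement in section 9.3.4 with the December 2013 to November 2023 schedule in the synopsis, because this decides how much data will lie beyond year 5.

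The cost is SAP wording and one extra table per parameter, from readings already collected. The downside is slightly fewer subjects in the change tables than in the visit-wise tables.
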